8.2 Randomization

Local randomization will take place such that each site can randomize subjects into either group without the need for central coordination. Separate randomization lists will be generated for each site in blocks of four, in order to reduce the possibility of an imbalance in group assignment. Randomization lists will be provided in a forthcoming Statistical Analysis Plan (SAP) to be completed prior to study initiation.

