- Subjects who are pregnant, nursing, or planning to become pregnant during the course of the study.
- Subjects who have known allergies to any ingredient(s) in the clinical products used in this study including silver.
- Subjects who do not wish to use product(s) derived from shellfish.
- Subjects with substance use disorder within the past six months.
- Subjects with active infection and/or currently receiving antibiotic treatment for the wound included in the study.
- Subjects who are currently enrolled in another research study which includes investigational treatment and/or medication.
- Subjects judged by the site PI or sub-investigator to be inappropriate as a subject of this study.
- Subject has previous or current systemic disease(s) which, in the judgement of the site PI, is likely to interfere with the study. However, subjects with well-controlled diabetes mellitus (DM) (HbA1c < 8.5) shall be permitted.
- Subjects who receive any additional product or procedure/activity that could influence wound healing, such as chemical debridement, use of other wound cleansers, additional hydrogel or alginate wound products etc.

Phase: Phase IV, Post-Market

Description of Sites/Facilities Multiple wound care centers

Enrolling Participants:

Description of Study Intervention: Subjects who meet all of the inclusion criteria and none of the exclusion criteria will be randomized to receive either MPS-Ag dressing or CMC-Ag dressing. The wound will be cleansed with Skintegrity® wound cleanser, followed by application of MPS-Ag dressing or CMC-Ag dressing. Compression bandage (CoFlex® TLC Two Layer Compression Bandage system) will be applied over the dressing. The dressings will be changed at least once weekly but can be changed earlier by the clinician depending on the level of exudate. Wound assessments will be carried out weekly. The performance of both the dressings will be evaluated according to the study objectives.

Study Duration: Six-to-Sixty months

Participant Duration: Subject participation is intended to last for eight weeks after application of the dressings. Participant duration will begin upon obtaining informed consent and will end after eight weeks or earlier if the subject's wounds heal completely prior to eight weeks.

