4. STUDY DESIGN

4.1. Overall Design

This study is a multi-site, open-label randomized clinical trial comparing MPS-Ag dressing to CMC-Ag dressing and determining which dressing better manages these lower extremity venous ulcer wounds. Subjects will be randomized to receive either MPS-Ag dressing or the CMC-Ag dressing. The wound will be cleansed with the wound cleanser and designated dressing will be applied on the wound. It will then be wrapped with the compression bandage. The dressings will be changed at least once every week but can be changed earlier by the clinician depending on the level of exudate. There will be no home dressing changes. Wound assessments will be carried out weekly, such as change in wound size and PUSAS score evaluation. Subject pain perception during every dressing change will be recorded. If the clinician feels that peri-wound tissue requires protection, a skin protectant may be applied by the clinician or the clinical staff, per the facility's standard of care and clinician's discretion. Dressing shrinkage after removal of the dressings will also be determined. The Schedule of Activities in Section 1.2 describes the timing and sequencing of the events.

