6.1.2 Eligibility Screening

Potential participants will be screened for eligibility via a combination of the screening form and by a review of the potential participant's wound(s) and medical chart by the site PI and/or their staff.

If the participant has multiple wounds, the site PI will select the wound that meets the inclusion criteria. If more than one wound meets all the inclusion criteria, the site PI will choose the most clinically appropriate wound for the application of the dressings and will make a note of it in the Subject Screening form and the CRF.

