6.2.4 Analgesic Usage

Since usage of analgesics will likely affect a subject's self-assessment of pain to dressing changes, analgesic usage will be recorded. This information will be recorded at the Initial Visit and all subsequent visits on the visit-specific CRFs.

After collecting all of the above information and data, the site PI or the qualified study staff will cleanse the wound, apply the designated dressing on the wound per the randomization schedule (see Section 8.2), and wrap it with compression bandage.

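### Open-label sites randomise locally in one fixed block size of four that the protocol discloses, so staff who track past allocations can often anticipate the next one

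*Combined protocol and SAP*

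**What the plan says.** Section 4.1 describes the design: "This study is a multi-site, open-label randomized clinical trial". Section 8.2 sets the allocation method. Sites randomise on their own ("Local randomization will take place such that each site can randomize subjects into either group without the need for central coordination"), and "Separate randomization lists will be generated for each site in blocks of four". No second block size is mentioned. On the lists themselves, 8.2 says: "Randomization lists will be provided in a forthcoming Statistical Analysis Plan (SAP) to be completed prior to study initiation". It does not say who may see them, who holds them, or how an assignment reaches the person enrolling.

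The protocol does give part of an order of events. The synopsis says "Subjects who meet all of the inclusion criteria and none of the exclusion criteria will be randomized". The schedule of activities puts screening on Day 0 and first application on Day 1. Under Section 6.1.2, if more than one wound qualifies, "the site PI will choose the most clinically appropriate wound for the application of the dressings and will make a note of it". Under Section 6.2.4, "After collecting all of the above information and data, the site PI or the qualified study staff will cleanse the wound" and then applies the dressing named by the schedule, with a reference back to 8.2.

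Several entry decisions are left to site judgement. The site PI decides whether the ulcer is venous and whether arterial circulation is adequate (5.1). The investigator may also rule a subject unsuitable (5.2).

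**The concern.** In an open-label trial, site staff see every earlier allocation at their site. If they also know the block size, they can count forward: the fourth assignment in a block is always determined, and sometimes the third. Someone who expects a particular dressing next may, deliberately or not, enrol, defer or exclude a borderline subject, or prefer one of two eligible wounds. Wounds with a better prognosis could then collect in one arm.

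Randomising only after eligibility is confirmed does not prevent this, because the anticipation comes from past allocations and is already available when eligibility is judged. Selection of this kind arises before baseline, and no analysis can be relied on to remove it fully.

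**Working it through.** **The plan's own figure.** The documents give no figure for predictability. The only related figure is the sample size in 8.1, used below as the setting: difference 40 − 33 = 7 points, SD 10, two-sided alpha 0.05, 1:1. The exact t-test power is 0.7997 at 66 subjects and 0.8116 at 68, so 68 is reproduced. The enrolment target is 80.

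**Predictability in a block of four.** A 1:1 block has 6 equally likely orders. For a guesser who knows the block size and the past allocations:

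| Position in block | Certain | Best guess correct |
|---|---|---|
| 1 | 0 | 0.500 |
| 2 | 0 | 0.667 |
| 3 | 1/3 | 0.667 |
| 4 | 1 | 1.000 |
| Mean | 1.333/4 = 33.3% | 2.833/4 = 70.8% |

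**Incomplete last blocks.** The number of sites is not given, so I assume 80 subjects split as evenly as possible.
- 4 sites of 20, or 10 sites of 8: all blocks complete, 33.3% certain.
- 8 sites of 10: 2 × 1.333 = 2.667 per site; 2.667/10 = 26.7%.
- 12 sites (8 of 7 subjects, 4 of 6): 8 × 1.667 + 4 × 1.333 = 18.67; 18.67/80 = 23.3%.

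**Illustrative bias.** Nothing in the documents says that steering occurs. Assume 68 subjects, 4 sites of 17, SD 10, no true difference, and steering of d = 2.5 points.
- Guess rate g per site, counting a tie as half: (4 × 2.833 + 0.5)/17 = 0.6961, so 2g − 1 = 0.392.
- All sites steer both ways in the same direction: 2d(2g − 1) = 5 × 0.392 = 1.96 points.
- One arm only is steered: d(2g − 1) = 0.98 points.
- Each site has a 50% chance of steering both ways: 0.5 × 1.96 = 0.98 points on average.

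The standard error of the difference is 10 × √(2/34) = 2.425. A shift of 1.96 is 0.81 standard errors, and the noncentral t gives a type I error of 12.5%. A shift of 0.98 is 0.40 standard errors and gives 6.8%. Simulation of 4,000 to 8,000 trials per setting agrees: about 12% to 13% when all sites steer, about 7% for one arm only, and 7.2% to 7.4% when each site has a 50% chance. With 12 sites all steering, the difference is 1.67 points and the error about 10%.

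**What varying the blocks would buy.** Blocks of 4, 6 and 8 were drawn at random, with the guesser assumed to know the set of sizes (exact sequence tree).
- Lists of 16: certain 2.5%, best guess 66.9%.
- Lists of 17: certain 2.4%, g = 0.6648. The all-sites difference becomes 5 × 0.3296 = 1.65 points, which is 15.9% less than 1.96.

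**The case against.** The strongest objection is that concealment may already be planned. Section 8.2 defers the lists to a SAP due before study start. That SAP is not in the supplied text and could name a custodian and a release method. This stands: on concealment, all that can be shown is that 8.2 is silent and has no cross-reference. It does not touch the fixed, disclosed block size, which is stated outright.

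The protocol also narrows the room for steering. Wound size and duration are numeric criteria (5.1). Area comes from a wound camera with image-analysis software, with a ruler only on malfunction (6.2.2). Monitoring covers eligibility and source data (9.1). A choice among wounds arises only when more than one qualifies. These points reduce the opportunity, but the judgements on diagnosis, arterial adequacy and suitability remain.

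A third objection is that steering is hypothetical and that the milder cases lie close to the nominal 5%. That is right, and the bias figures show what is possible, not what is likely. The predictability figures need only tracking and knowledge of the block size.

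Two stronger readings are tempting. A reader might infer that the lists are printed in the protocol, or that enrolling staff can read them. Only the block size is printed; the lists are due in the SAP, and no document says who will have access. A reader might also infer that the trial has no concealment, which silence in 8.2 does not establish.

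**Conclusion.** The point holds as a weakness of design that should be corrected. One fixed block size of four, disclosed in the protocol of an open-label trial with local site lists, makes 33.3% of assignments certain and 70.8% guessable in complete blocks. The certain share is lower if sites are many and small (23.3% for 80 subjects at 12 sites). This assumes that staff know the block size and track all earlier allocations at their own site.

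The step from predictability to bias rests on assumptions that the documents neither support nor exclude. Under those used here, the false difference is about 1 point with about 7% type I error, or about 2 points with 12% to 13% if every site steers both ways in the same direction. The planned effect is 7 points. None of this shows that selection has occurred or will occur, and the sample size of 68 is unaffected.

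**What to change.** Revise Section 8.2 as follows.

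1. Keep the separate site lists, but replace the fixed block of four with randomly varying block sizes (for example 4, 6 and 8) that are not disclosed to sites. Delete the block size from the protocol.
2. Keep the lists out of any SAP version that sites can see, and hold them in a restricted file.
3. State that each assignment is released by sequentially numbered opaque sealed envelopes, or an equivalent, only after consent, eligibility, the chosen study wound and the baseline area are recorded. The order in the synopsis and in 6.1.2 and 6.2.4 is already compatible. If the SAP already says this, a cross-reference is enough.

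Varied blocks mainly remove certain knowledge. Best guesses fall only from about 71% to about 67%, so some predictability remains.

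The cost is modest: revised wording, new lists, envelopes or an equivalent, and a restricted file. Within-site balance loosens slightly, to a mean arm difference of about 0.5 subjects per site at 4 sites of 20, against 0 with complete blocks of four. If the study is already running, the change needs an amendment and can apply only to later subjects.

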8.3 Populations for Analyses

An evaluable population will be used for all analyses, with evaluable defined as any subject with valid initial visit and final visit wound size measurements.

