1.2 Schedule of Activities (SOA)

REQUIRED ASSESSMENTS & ACTIVITIES	Screening Visit Day 0	Initial Visit Day 1	Weekly visits (combined with dressing change visits) (Every 7 days ± 2 days)	Unscheduled Dressing change visits –	Final Visit (8 weeks from initial visit) ^{a,d}
Informed consent and screening form	X				
Wound assessment for eligibility	X				
Demographics and review of medical history		X			
List of medications taken by the subject		X	X	X	X
Application of new MPS-Ag or CMC-Ag dressings that will be compression wrapped ^b		X	X ^c	X ^c	
Pain assessment during removal and application of MPS-Ag dressing or CMC-Ag dressing, and dressing shrinkage evaluation		X ^{e,f}	X	X	X
Wound assessment (physical examination and infection evaluation)		X	X	X	X
Take wound photographs, record wound size and PUSAS score		X	X		X
Record analgesic use		X	X	X	X
Adverse event assessment		X-----X			

a: If the subject's wound heals prior to eight weeks, their participation in the study will be terminated. b: Dressings will be changed at least once weekly but can be changed earlier by the clinician depending on the level of exudate. c: MPS-Ag or CMC-Ag dressings will be removed, followed by application of a new MPS-Ag or CMC-Ag dressing, which will then be compression wrapped. d: Dressings will be removed, without application of a new MPS-Ag or CMC-Ag dressing, on the final day and all the assessments will be carried out. e: Pain assessment will be carried out only during application of MPS-Ag or CMC-Ag dressings on initial visit. f: Dressing shrinkage evaluation will not be carried out in the initial visit.
					

Comparison of marine polysaccharide and carboxymethylcellulose dressings

MED-2018-DIV71-026

30-JUN-2022

V 4.0

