6.3.2 Infection evaluation

During dressing change visits, the wound site included in the study will be evaluated for development of any infection. In the event of a suspected infection, clinical staff will collect a wound culture. Should a subject develop an infection as confirmed by wound culture, this will be noted as an adverse event (AE) and his or her participation in the study will be terminated. Subject participation will also be terminated if they receive any antibiotic, prophylactic or therapeutic, for treatment of the wound site included in the study.

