6.3.3 Dressing shrinkage evaluation

Dressing shrinkage, if any, will be evaluated by measuring surface areas of the dressings at the time of their application and during their removal.

6.4 Wound assessment visits – Weekly visits (Every 7 days \pm 2 days) and final visit

Subjects must undergo dressing changes and wound assessments once every week. Analgesic(s) use will be recorded, and subjects will be asked to report any change in medication during their visits. Assessments carried out will be identical to those described in sections 6.2.2, 6.2.3, and 6.2.4, and sections 6.3.1, 6.3.2, and 6.3.3. The final visit will be the visit eight weeks from the subject's initial visit or whenever the wound is healed (whichever happens first). Dressings will be removed, and all the assessments will be carried out. Information will be recorded on the CRFs.

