8.4 Data Analysis

Descriptive statistics will be provided for the key endpoints, including measures of central tendency (mean or median, as appropriate), measures of variation (standard deviations, coefficients of variation) and 95% confidence intervals and interquartile ranges, as appropriate. Specifically, these measures will be calculated for:

- Changes in wound size
- Average percent periwound global score reduction
- Subject's pain rating during dressing changes
- Dressing shrinkage determined upon removal of dressings
- Proportion of subjects who develop an infection

The key assessment for differences in dressing performance will be based on the comparison of mean reduction in wound size for each dressing type. The specific details of the statistical testing will be provided in a forthcoming SAP. Comparisons of reduction in PUSAS score, subject pain ratings, and dressing shrinkage will also be made between the two dressing types, with specific details described in the SAP.

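### Section 8.3's single evaluable set keeps early healers and drops early failures from the primary comparison, and it omits earlier infections from the planned infection proportion

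*Combined protocol and SAP*

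**What the plan says.** Section 8.3 defines one population: "An evaluable population will be used for all analyses, with evaluable defined as any subject with valid initial visit and final visit" wound size measurements. No all-randomised set, safety set or missing-data rule appears elsewhere in the document.

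Section 6.4 places the final visit eight weeks from the "initial visit or whenever the wound is healed (whichever happens first"). Footnote a of the schedule (section 1.2) agrees: if the wound "heals prior to eight weeks, their participation in the study will be terminated". An early healer therefore has a final visit.

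Section 6.3.2 covers the unfavourable exits. After a culture-confirmed infection, "his or her participation in the study will be terminated". It adds: "Subject participation will also be terminated if they receive any antibiotic, prophylactic or therapeutic, for treatment of the wound site" in the study. Section 4.2 adds a significant medical condition that precludes continuation, and withdrawal, and says withdrawn subjects are replaced. Neither the text nor the schedule provides an early-termination visit.

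Section 8.4 bases the key assessment on mean reduction in wound size by dressing. Its list of summaries includes "Proportion of subjects who develop an infection". It leaves the details of testing to a forthcoming SAP.

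**The concern.** Inclusion in the primary analysis depends on what happens after randomisation. A subject whose wound closes in week 3 is analysed. A subject who leaves in week 3 with an infected wound is not. Section 4.1 describes a "multi-site, open-label randomized clinical trial comparing MPS-Ag dressing to CMC-Ag dressing", and several exits involve site judgement: suspecting infection, giving an antibiotic, deciding that a condition precludes continuation. Exit could therefore differ by arm, and the analysed groups would then no longer be the randomised ones. The 12 extra subjects in 8.1 and the replacements in 4.2 restore numbers, not comparability.

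The infection summary has a separate fault. Infection ends participation, and anyone whose participation ends before the final visit leaves the denominator. The summary thus excludes many of the subjects it is meant to count.

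**Working it through.** **1. The plan's own figure.** Section 8.1 gives 40% versus 33% reduction, SD 10, two-sided alpha 0.05, 1:1 allocation. With the noncentral t distribution, 33 per arm gives 79.97% power and 34 per arm gives 81.2%, so 68 is reproduced. 68/(1 − 0.15) = 80, which leaves 12 subjects for incomplete data of any cause. The sample size is not in question.

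**2. Who is evaluable, read literally.**

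| Route out of the study | Final visit? | Analysed? |
|---|---|---|
| Completes 8 weeks | yes | yes |
| Heals early | yes | yes |
| Culture-confirmed infection before the final visit | no | no |
| Antibiotic for the study wound before the final visit | no | no |
| Precluding medical condition before the final visit | no | no |
| Withdrawal before the final visit | no | no (replaced) |

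**3. Evaluable versus all-randomised difference.** Assumptions: 40 per arm; evaluable means 40 and 33; *a* MPS-Ag and *b* CMC-Ag subjects lost, 12 in total; lost subjects average *x* = 0 to 20% reduction.

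D = [(40 − a)·40 + a·x]/40 − [(40 − b)·33 + b·x]/40

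| a, b | x = 0 | x = 20 |
|---|---|---|
| 6, 6 | 34.00 − 28.05 = 5.95 | 37.00 − 31.05 = 5.95 |
| 8, 4 | 32.00 − 29.70 = 2.3 | 36.00 − 31.70 = 4.3 |
| 4, 8 | 36.00 − 26.40 = 9.6 | 38.00 − 30.40 = 7.6 |

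The evaluable set shows 7 in every row.

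**4. Identical arms.** Let each arm of 40 have mean 33 and contain 8 poor responders averaging *x*. The other 32 average g = (40·33 − 8x)/32, which is 41.25 for x = 0 and 36.25 for x = 20. One arm loses all 8. The other loses 4 and keeps 4, so its evaluable mean is (32g + 4x)/36.

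- x = 0: 41.25 − 36.67 = 4.58 points.
- x = 20: 36.25 − 34.44 = 1.81 points.

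With a within-group SD of 10, the arm that keeps four poor responders has SD √[100 + (4/36)(32/36)(g − x)²], which is 16.4 and 11.2 respectively. In simulation (60,000 trials, equal-variance t-test, 32 versus 36 subjects) the nominal 5% test rejects about 20% and 9% of the time. If the SD were 10 in both arms, the figures would be 46% and 11%. Equal loss gives no expected difference.

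**5. Infection proportion.** Assume a constant weekly hazard, no healing, and a true 8-week risk *p*. Then h = 1 − (1 − p)^(1/8). The evaluable set is those infection-free through week 7, so the reported proportion is h. The share of infected subjects omitted is 1 − (1 − h)⁷·h/p.

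| True p | Reported | Omitted |
|---|---|---|
| 5% | 0.6% | 87.8% |
| 15% | 2.0% | 88.4% |
| 20% | 2.8% | 88.7% |
| 40% | 6.2% | 90.1% |

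**6. Power if early exits are included.** This illustrates one method: a t-test, 40 per arm, equal loss fraction *f*, exits assigned a mean of 20% reduction with SD *s*. Arm mean = (1 − f)μ + 20f. Variance = (1 − f)·100 + f·s² + f(1 − f)(μ − 20)².

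- f = 0.10: difference 6.3; power 73.5% (s = 0) or 69.9% (s = 10).
- f = 0.15: difference 5.95; power 66.5% (s = 0) or 61.5% (s = 10).

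**The case against.** - **A SAP is still to come.** It could add populations or missing-data rules. However, 8.4 defers test details, whereas 8.3 fixes the population for all analyses and defers nothing.
- **Sites might treat an exit assessment as the final visit.** Fewer subjects would then be dropped. Section 6.4 and the schedule do not say this; if it is intended, it must be written.
- **Not every infection leads to exclusion.** This stands. A suspected infection that is neither culture-confirmed nor treated with an antibiotic stays in. Section 4.2 can also be read as tying infection exits to the site investigator's opinion, while 6.3.2 is categorical; the two passages need reconciling. The documents give no infection timing, so the omitted share in step 5 is conditional on its assumptions.
- **The infection summary carries little weight.** Largely true. It is descriptive, it is not a primary or secondary endpoint, and the infections are still recorded as adverse events.
- **The unequal-loss scenarios are chosen, not observed.** This stands. Section 8.1 assigns the 12 to any cause, not to treatment failure, and nothing supports a 2:1 split. Active infection and current wound antibiotics are excluded at entry, and both dressings contain silver.
- **An all-randomised analysis does not remove the bias.** Also true. Nothing is measured after exit, and carrying the last area forward sets a week-1 exit beside week-8 completers.

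**Conclusion.** The defect holds on the text. Followed as written, the primary comparison is conditioned on a post-randomisation outcome, and the infection proportion omits confirmed or treated infections found before the final visit. The primary comparison is what makes this important. It should be settled before the arms are compared, including at the n = 46 interim analysis in 8.5.

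The size is unknown because no exit rates by arm are given. Under the stated assumptions, an evaluable difference of 7 points could correspond to anything from 2.3 to 9.6 points in all randomised subjects, and equal loss moves it only to 5.95.

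A reader might infer more than the documents support:

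- *That the result will favour the sponsor's dressing.* The direction depends on which arm loses more subjects.
- *That false positives could approach one in two.* The 46% figure needs an SD of 10 in both arms. If the arms are truly identical and one merely keeps its poor responders, the range is about 9–20%.
- *That infection data are lost.* They remain in the adverse event records; the planned proportion is what is wrong.
- *That about 90% of infections are certain to be omitted.* That share comes from an assumed constant hazard.

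**What to change.** Replace 8.3 with the following:

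1. **Infection and adverse events:** all subjects who received a study dressing.
2. **Primary:** all randomised subjects with a baseline wound size, in the assigned arm, using the weekly areas already scheduled (healed = 0 cm²), on the percentage-reduction scale of 2.1 and 8.1. Prespecify the early-exit rule. It must cover subjects with no post-baseline area, because the schedule row "Take wound photographs, record wound size and PUSAS score" is not marked for unscheduled visits. Possible rules, neither required, are a longitudinal model with baseline among the responses, or the last area before exit with 0% change if there is none. A model of raw areas would also need a stated route to percentage reduction.
3. **Sensitivity analyses:** 0% reduction for infection or antibiotic exits, and the current evaluable set.
4. **Section 4.2:** state that withdrawn subjects stay in the analysis even if replaced, and whether withdrawal covers terminations for infection or antibiotics.

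This reduces selection but does not eliminate bias.

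The cost is wording and analysis work, with no new visits or measurements, and a less favourable stated power. Step 6 shows the order of the loss for one method; it does not apply to the longitudinal model. Compute power for the method chosen and restate it. This point does not require added enrolment; whether to accept the lower power is the sponsor's decision.
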